#### Study end/ Final visit for second and third key secondary endpoints

Please refer to [Section 7.5.1](#) for the derivation.

#### Rescue medication in general:

Rescue medication is defined as any dose increase of anti-diabetic background medication (as compared to one day prior to first drug administration) or introduction of new anti-diabetic treatment, for insulin any new onset and intake for at least 15 days, starting from the date of first drug administration until the time as specified in [Section 6.8.3](#).

In general, any therapy with the start date equal to the date of first trial drug intake is considered as being taken after first trial drug intake.

If a patient switches to or adds protocol defined background medication at or after the date of first trial drug intake, this will be considered rescue medication. (The same applies for a change from metformin or alpha-glucosidase inhibitor to metformin + alpha-glucosidase inhibitor.)

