### 3. DESCRIPTION OF DESIGN AND TRIAL POPULATION

#### 3.1 OVERALL TRIAL DESIGN AND PLAN

This multicentre, multinational, randomised, double-blind, parallel group, comparator-controlled study compares treatment with linagliptin (5 mg once daily) to treatment with glimepiride (1-4 mg) as monotherapy or as add-on therapy to metformin and/or other antidiabetic treatment as specified in Section [3.3.2](#).

The trial is event driven and will run with an estimated number of 6000 patients for an estimated treatment time of 432 weeks, beginning with the randomisation of the first patient. In the case the number of events is not or may not be reached within this period the trial duration and/or the number of patients enrolled will be increased until the defined number of adjudicated primary events is reached.

Patients will enter an open-label placebo (add-on) run-in period of 2 up to 4 weeks before randomisation. Patients who successfully complete at least two weeks of the placebo-run (should have a treatment compliance between 80% to 120%) and who still meet the inclusion/exclusion criteria will be randomised to receive either linagliptin or glimepiride. Patients who do not successfully complete at least two weeks of the placebo run-in, may continue the placebo run-in phase up to four weeks to meet the compliance criterion as specified above. Any SU or glinide will be discontinued at randomisation Visit 2 (SU/glinide should not be taken in the morning of Visit 2).

The randomised treatment will be double-blind within the dose groups of linagliptin and glimepiride (i.e. each patient will receive one active treatment and placebo matching the alternative active treatment in a double-dummy design).

[figure not shown]

Figure 3.1: 1 Treatment periods and treatment groups in the trial design

For all patients, contacts are scheduled at regular time intervals ([see flow chart](#)). The estimated treatment duration for the first randomised patient is 432 weeks. The End of Treatment Visit (EOT) activities will be performed when a patient discontinues study medication permanently. Patients who discontinue study drug prematurely should be observed until study end as if they were still receiving blinded study treatment, but no (safety) laboratory sampling (including pregnancy test), ECG or vital signs will be required. If a patient who prematurely discontinued study drug is not willing to return

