#### 4.1.4 Drug assignment and administration of doses for each patient

Following the screening period and the placebo run-in period, patients who qualify will be randomised (Visit 2) to one of the dosage and treatment schedules outlined in [Table 4.1.4: 1](#) below. Medication will be dispensed in a double-blind and double-dummy manner as either 5 mg linagliptin (plus glimepiride placebo) or an initial dose of 1 mg /day of glimepiride (plus linagliptin placebo). IXRS will allocate medication kit numbers at each scheduled in-clinic visit (V2 – 31). At visits 2-5 patients will receive one treatment box, sufficient for 4 weeks treatment (plus 1 week reserve). At visits 6- 31 patients will receive one treatment box, sufficient for 16 weeks (plus two weeks reserve) of treatment.

After the starting dose of 1 mg/day, glimepiride/ glimepiride placebo has to be uptitrated in 4 week intervals during the first 16 weeks of treatment to the next dose to a potential maximum dose of 4 mg/day, if the fasted HBGM values are > 110 mg/dl (6.1 mmol/l) at the day of visit 3, 4 and 5 (in-clinic HBGM measurement at the day of the visit), unless the investigator considers that it would place the patient at an increased risk for hypoglycaemia. The average HBGM value of previous recent fasting HBGM measurements prior to the day of visit (from the patient's HBGM diary) could also be used to guide uptitration at the discretion of the investigator, if there is a meaningful discrepancy between the single fasted HBGM value at the day of the visit in the clinic and this average HBGM value.

Patients on previous glimepiride may continue on their previous glimepiride dose up to Visit 2 (SU/glinide should not be taken in the morning of Visit 2). These patients will start the glimepiride/glimepiride placebo at their pre-trial glimepiride dose. If prior glimepiride dose was  $\geq 4$  mg/day, the patient will start the glimepiride/glimepiride placebo in the randomisation phase at a dose of 4 mg/day combined with 5 mg/day linagliptin/ linagliptin placebo. Patients on a previous SU, that is not glimepiride, or glinide should start glimepiride /glimepiride placebo at Visit 2 at a starting dose of 1 mg/day combined with 5 mg/day linagliptin/ linagliptin placebo.

The patients will be instructed to bring their HBGM devices to a visit for an additional measurement of fasted glucose during the titration phase, and if required, during maintenance phase ([see flow chart](#)).

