#### Key Secondary endpoints

As key secondary endpoints will be analysed:

- 1) time to the first occurrence of any of the following adjudicated components of the composite endpoint: CV death (including fatal stroke and fatal MI), non-fatal MI (excluding silent MI), non-fatal stroke or hospitalisation for unstable angina pectoris.

- 2) composite endpoint of (treatment sustainability defined as the proportion of patients that are on study treatment at study end, that at Final Visit maintain glycaemic control ( $HbA1c \leq 7.0\%$ ) without need for rescue medication\* (between end of titration [Visit 6] and Final Visit) and patients without any moderate/severe hypoglycaemic episodes (between Visit 6 and Final Visit) and without  $> 2\%$  weight gain at Final Visit (between Visit 6 and Final Visit)).
- 3) composite endpoint of (treatment sustainability defined as the proportion of patients that are on study treatment at study end, that at Final Visit maintain glycaemic control ( $HbA1c \leq 7.0\%$ ) without need for rescue medication\* (between Visit 6 and Final Visit) and patients without  $> 2\%$  weight gain at Final Visit (between Visit 6 and Final Visit))

\* Any dose increase of anti-diabetic background medication or introduction of new anti-diabetic treatment during study medication treatment will be counted as rescue medication. Short term use of any insulin- up to two weeks - (e.g. during hospitalisation) won't count as rescue medication in the definition of treatment sustainability.

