B2	Informed consent given too late	Date of informed consent for the study not obtained prior to any study related procedure. Minimum requirement for initial informed consent <= date of Visit 1a/date of any study procedure	R/S	None
C	Trial medication and randomisation			
C1	Incorrect Trial Medication Taken			
C1.1	No study medication taken	Patient randomised, but no study medication taken.	E	TS, OS, PPS

Table 6.2: 1 (cont'd.) Important Protocol Violations

Category / Code	Description	Comment/Example	Affects rights or safety (R/S) or primary/ key secondary outcome (E)	Excluded from
C1.2	Incorrect trial medication taken	Wrong medication (different medication than the patient was randomised to) taken for more than 20% of the overall treatment duration of a patient. This is identified by the medication kit number recorded in eCRF as well as the medication kit number as assigned by IXRS. Can also be manually identified by investigator or CRA. Can only be finally judged after DBL since unblinding information is required.	E	PPS
C2	Randomisation not followed			
C2.1	Treated before calling IXRS	Date of randomisation call after date of study drug intake at visit 2	E	PPS
C3	Non-compliance			
C3.2	Non-compliance with criteria for removal from study medication	This includes only the following case: although a patient is pregnant, she is treated. A missing pregnancy test does not qualify as IPV.	R/S	None

Table 6.2: 1 (cont'd.) Important Protocol Violations

Category / Code	Description	Comment/Example	Affects rights or safety (R/S) or primary/ key secondary outcome (E)	Excluded from	
D	Concomitant Medication				
D1	Improper medication washout				
	D1.1	Glinide or SU not stopped until 35 days after first study drug intake	For patients on SU/glinide at baseline: Date of termination of glinide or SU > Date of first trial drug intake + 35 days	E	PPS
D2	Prohibited medication use during the treatment period of the trial	Not applicable.			
D3	Mandatory medication not taken	Not applicable.			
E	Missing data	Not applicable.			
F	Incorrect timing	Not applicable.			
G	Trial specific protocol violations				
	G1.1	Previous participation within this study		E, R/S	PPS
	G1.2	Serious non-compliance potentially affecting primary endpoint*		E, R/S	PPS*

**Note:** Missing visits, evaluations, and tests will be considered missing data, not protocol deviations.

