### Concomitant medication

All frequency tabulations will be performed on the TS.

In general, any therapy with the start date equal to the date of first trial drug intake is considered as being taken after first trial drug intake.

Overall concomitant medication use (excluding antidiabetic/background therapy) with an incidence of  $\geq 1\%$  in at least one treatment group per WHO-DD preferred name will be summarised by Anatomical-Therapeutic-Chemical classification level 3 (ATC3). Summaries will be presented for concomitant therapies taken during screening and those taken after first drug intake.

Separate summaries of use of acetylsalicylic acid (ASA), antihypertensives, lipid lowering drugs, P-gp or CYP 3A4 inhibitors and anti-coagulants during screening and those taken after first drug intake will be presented.

Antidiabetic therapies including background therapies taken at screening as well as those started after the date of first trial drug intake will be presented, with categorisation into monotherapy/combination therapy and the number of (oral) antidiabetic drugs. Antidiabetic therapies at screening will be linked to the visit 1a HbA1c to reflect the different categories of inclusion criterion 2.

An antidiabetic therapy that is not a background therapy is considered as being taken at screening, if the start date was before the date of IC and the end date was not earlier than 10 weeks prior to IC. As the start and stop date of the protocol-defined background medication of alpha-glucosidase inhibitor and/or metformin is not recorded in the eCRF, it is assumed, that this background medication was already taken at screening.

Summaries on the total daily dose of metformin at the date before first trial drug intake and last date of trial drug intake will be provided, this includes a categorisation into  $\leq 1500\text{mg}$  or  $>1500\text{mg}$ .

The number of patients with a change in background therapy at any time starting from the date of first intake of trial drug will be presented for metformin as well as alpha-glucosidase inhibitor.

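### A sulphonylurea or glinide that is never stopped at randomisation does not count as rescue, so the patient can be a responder on key secondary endpoints 2 and 3

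*SAP*

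**What the plan says.** **Endpoints.** Under SAP 5.2.1, a responder on key secondary endpoint 3 is on study treatment at study end, has HbA1c of 7.0% or less at Final Visit, has needed no rescue between Visit 6 and Final Visit, and has not gained more than 2% in weight. Endpoint 2 also requires no moderate or severe hypoglycaemia.

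**Rescue.** The SAP definition has two limbs. The first is a dose increase: "Rescue medication is defined as any dose increase of anti-diabetic background medication (as compared to one day prior to first drug administration"). The second is "or introduction of new anti-diabetic treatment, for insulin any new onset and intake for at least 15 days". On timing, "any therapy with the start date equal to the date of first trial drug intake is considered as being taken after first trial drug intake". Protocol 7.1 has the same two limbs: "Any dose increase of anti-diabetic background medication or introduction of new anti-diabetic treatment during study medication treatment will be counted as rescue medication".

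**Prior SU or glinide.** These patients are eligible under inclusion criterion 2b. Protocol 3.1 states "Any SU or glinide will be discontinued at randomisation Visit 2", and Protocol 4.1.4 adds "Patients on previous glimepiride may continue on their previous glimepiride dose up to Visit 2". The drug is therefore normally still in use on the day before first study drug.

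**Failure to stop.** SAP Table 6.2: 1, code D1.1, reads "Glinide or SU not stopped until 35 days after first study drug intake". It is marked as affecting the primary or key secondary outcome, with exclusion from the per-protocol set (PPS) only. Code D2, prohibited medication, is marked not applicable.

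**Analysis.** Endpoints 2 and 3 are tested with a chi-square test on the treated set (TS) (SAP 6.3 and 7.5.1). The PPS and on-treatment set (OS) serve sensitivity analyses.

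**The concern.** The two endpoints ask whether randomised treatment sustains glycaemic control without added glucose-lowering therapy. The rescue rule treats two similar patients differently: one who starts an SU after first study drug fails the endpoint, while one who never gave up the prior SU does not.

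On linagliptin, the second patient's control may owe something to the comparator's own drug class. On glimepiride, the patient is taking two drugs of that class. In either arm the response is credited to randomised treatment alone. Endpoint 3 is the more exposed because it has no hypoglycaemia criterion to remove some of these patients.

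**Working it through.** The plan gives no expected response rate, power or sample size for endpoints 2 and 3, so there is no planned figure to reproduce. The check is one of logic, followed by an illustration of size.

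**Step 1: apply the rule.** Rescue = (dose after first drug > dose on the day before) or (treatment newly introduced from first drug on).

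| Case | Dose increase? | New treatment? | Rescue? |
|---|---|---|---|
| SU continued at the same dose | no | no | no |
| SU dose raised | yes | no | yes |
| SU first started after first drug | no prior dose | yes | yes |

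The first row does not depend on whether SU counts as background medication. If it does, its dose has not risen. If it does not, which SAP 7.2 suggests by speaking of "protocol-defined background medication of alpha-glucosidase inhibitor and/or metformin", it is still not newly introduced.

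**Step 2: look for another rule that catches the patient.**
- The non-responder rules in SAP 7.5.1 name permanent treatment stop and death, not continued SU.
- D2 is not applied.
- D1.1 acts only on the PPS. Its test compares a termination date with first intake plus 35 days, and a patient who never stops may have no such date.
- The TS and OS definitions in SAP 6.3 do not exclude the patient.

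Nothing in the visible text reclassifies this patient in the confirmatory analysis.

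**Step 3: size.** The protocol synopsis gives 3000 patients per arm. Let f be the share of an arm that never stops SU or glinide, and q the share of those who meet every other responder criterion. Both are assumptions; the documents give neither. Wrongly credited responders per arm = 3000 × f × q, and the shift in that arm's response rate is f × q.

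| f | q | Never stop | Credited | Shift (points) |
|---|---|---|---|---|
| 0.2% | 10% | 6 | 0.6 | 0.02 |
| 0.5% | 20% | 15 | 3 | 0.1 |
| 1% | 20% | 30 | 6 | 0.2 |
| 2% | 40% | 60 | 24 | 0.8 |
| 5% | 40% | 150 | 60 | 2.0 |

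The last row is extreme. If 20% to 40% of an arm were prior SU or glinide users (also an assumption), f = 5% would mean that 5/40 = 12.5% to 5/20 = 25% of them never stopped.

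The shift in the treatment difference is f × q in the linagliptin arm minus f × q in the glimepiride arm. It is zero if both are equal. If f is 1% in both arms and q is 20% in one and 40% in the other, it is 0.01 × (0.40 − 0.20) = 0.2 points, and its sign is unknown.

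**Step 4: scale.** The smallest difference significant at a nominal two-sided 0.05 is 1.96 × √(2p(1−p)/3000): 1.52, 2.02 and 2.32 points at response rates p of 10%, 20% and 30% (also assumed). The level actually available is lower once alpha has been spent at the interim analyses, so the real thresholds are somewhat higher.

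**The case against.** The strongest reply is that this concerns a narrow protocol deviation already provided for. SU and glinide must stop at Visit 2, Protocol 4.2.2.1 prohibits other antidiabetic agents, and concomitant therapy is reviewed at every visit. To be wrongly credited, a patient must keep taking the drug beyond Visit 6, remain on study drug to the end, and meet every other criterion. D1.1 identifies such patients and the PPS analysis is meant to leave them out. Keeping deviators in the TS follows the as-randomised principle, and the SAP follows the protocol's definition.

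Most of this stands, and it limits the size of the problem. It does not remove the gap. Staying in the TS settles who is analysed, not how a response is scored, and these endpoints themselves make added glucose-lowering therapy a failure.

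A reader might go further in three ways that the documents do not support.

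- *That the reference day is the cause.* A patient who never stops escapes on the words dose increase and new, whichever pre-drug day is the reference.
- *That a patient who stops and later resumes SU also escapes.* The SAP does not address this case expressly. But if SU is background medication, adding it after first drug is rescue under SAP 5.2.1; if it is not, a restart most naturally reads as a new treatment.
- *That the error favours linagliptin by up to about one standard error.* That needs 40% prior users, 5% of them continuing or resuming and 40% of those responding (3000 × 0.4 × 0.05 × 0.4 = 24 patients, 0.8 points, against a standard error of 0.77 to 1.18 points), with all 24 on linagliptin. Failure to stop at Visit 2 occurs under double-blind, double-dummy treatment and should start out balanced.

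**Conclusion.** The gap is real but narrow. As written, the rescue rule misses an SU or glinide carried past Visit 2 unchanged, and the confirmatory TS analysis of endpoints 2 and 3 can score that patient as a responder, although the SAP itself marks the deviation as outcome-affecting.

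The number of such patients is not given. Under the assumptions above, one arm's response rate moves by 0.02 to 2.0 points, with the top of that range implausible, and the treatment difference moves by less unless the deviation is unbalanced. The effect is probably small and no direction can be claimed. Endpoint 2 is the fourth step of the hierarchy and endpoint 3 the fifth, so neither is confirmatory unless non-inferiority and superiority on the primary endpoint and superiority on the first key secondary endpoint have all been shown.

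The conclusion rests on the rescue definition and non-responder rules in the public text, which contain no exception for this case.

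**What to change.** Add one sentence to SAP 5.2.1: for the sustainability component of key secondary endpoints 2 and 3, any open-label SU or glinide taken between Visit 6 and Final Visit counts as rescue medication, whether continued from before randomisation or restarted, and whatever the dose on the day before first study drug. This also settles the restart case explicitly.

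Keep the rule to that window. The D1.1 tolerance ends at day 35 and Visit 6 is planned at day 112, so an SU stopped before Visit 6 should not be classed as rescue. A rule that ran from day 36 and extended to time to rescue and to the OC and LOCF handling of HbA1c and FPG would do harm. The first scheduled on-treatment HbA1c is at Visit 6. A patient who stopped SU on day 40 and then followed the protocol would lose every later HbA1c value in the OC analysis, and would have baseline carried forward under LOCF (SAP 6.6).

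The cost is one sentence, using therapy dates that D1.1 already needs. The downside is that a few deviators become non-responders. This is an analysis classification and changes no patient's treatment.

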#### Moderate and severe hypoglycaemic episodes are defined as follows:

A moderate hypoglycaemic event is defined as documented symptomatic hypoglycaemia with plasma glucose concentration  $\leq$  70 mg/dL, without the need for external assistance.

A severe hypoglycaemic event is defined as documented hypoglycaemic episode requiring assistance of another person to actively administer carbohydrate, glucagon or other resuscitative actions need for external assistance.

## **5.2.2 (Other) Secondary endpoints**

### **5.2.2.1 Secondary cardiovascular endpoints**

Secondary CV endpoints are:

- occurrence of at least one of the following CEC confirmed adjudicated components of CV death (including fatal stroke and fatal MI), non-fatal MI (excluding silent MI), non-

fatal stroke and hospitalisation for unstable angina pectoris

This endpoint will be further referred to also as ‘occurrence of 4P-MACE’.

- occurrence of at least one of the following CEC confirmed adjudicated components of CV death (including fatal stroke and fatal MI), non-fatal MI (excluding silent MI) and non-fatal stroke  
This endpoint will be further referred to also as ‘occurrence of 3P-MACE’.
- occurrence of and time to the first occurrence of any of the following components of the composite endpoint of all CEC confirmed adjudicated events of:
  - CV death (including fatal stroke and fatal MI)
  - non-fatal MI
  - non-fatal stroke
  - hospitalisation for unstable angina pectoris
  - TIA
  - hospitalisation for congestive\* heart failure
  - hospitalisation for coronary revascularization procedures (CABG, PCI)

\*refers to all heart failure events as adjudicated and confirmed by CEC and will be referred to as ‘heart failure’ in the CTR

#### 5.2.2.2 Secondary diabetes related endpoints

Secondary diabetes related endpoints include change from baseline to Final Visit in the following laboratory parameters:

- HbA1c
- Fasting plasma glucose
- Total cholesterol
- LDL cholesterol
- HDL cholesterol
- Triglycerides
- Creatinine
- eGFR (MDRD formula)
- Urinary albumin

In addition any transition in albuminuria classes will be investigated by using UACR. Please refer to [Table 7.8.2: 2](#) for the definition of classes.

For these endpoints, the final visit value refers to the last value obtained on treatment. Parameter-specific on-treatment phases are defined according to [Section 6.7.2](#). The intake of rescue medication is considered as described in [Section 5.2.1](#).

## 6. GENERAL ANALYSIS DEFINITIONS

### 6.1 TREATMENTS

The following treatments are investigated in this study:

Table 6.1: 1 Treatments and labels used in the analysis

Treatment	Short label
A Linagliptin tablet 5 mg / Placebo Glimperide capsule 1-4 mg	Lina
B Glimperide capsule 1-4 mg / Placebo Linagliptin tablet 5 mg	Glim

